9.1.3 Self-Controlled Designs

The Self-Controlled designs use individuals who experienced the <<event>> in a pre-specified time window, which will be split into at-risk time and reference (control) time. Each subject serves as his/her own control, thus controlling for fixed potential confounders.

[figure not shown]
A pre-specified risk period will be required considered for each of the events under evaluation after any <<COVID-19 vaccine>> dose. The risk period depends on the type of event as specified above.

9.1.3.1 Self-controlled Case Series (SCCS)

Retrospective (multi)-database case-only study that includes subjects who were vaccinated with << COVID-19 vaccine>> and experienced << event>>.

The incidence rate ratio between a period of time hypothesized to be at increased risk due to exposure (“risk window”) and control window (All other time within an individual's observation period, that does not fall within the risk period) is calculated (Figure 3).

Figure 3. Self-Controlled Case Series

[figure not shown]

9.1.3.2 Self-Controlled Risk Interval (SCRI)

Retrospective (multi)-database case-only study including subjects who were vaccinated with <<COVID-19 vaccine>> and experienced << event>>.

The risk and control windows should be pre-specified. The incidence rate ratio between a period of time hypothesized to be at increased risk due to exposure (“risk window”) and control window (a pre-specified time window occurring after the risk window) is calculated. The SCRI is a subtype of the SCCS design, with a pre-specified duration of the control period (Figure 4).

Figure 4. Self-Controlled Risk Interval design

[figure not shown]

Note: Example with a risk period of 42 days and a control period of 42 days

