For example, for the evaluation of Guillain Barre Syndrome (GBS), a follow-up time period of at least 42 days should be applied after vaccine dose 1. In case a second/third vaccine dose is recommended or inadvertently administered, the follow-up period should be classified by dose and be extended for an additional 42 days after dose 2/3.

As a second example, for the evaluation of anaphylaxis, a risk period of 48 hours should be considered after each vaccine dose.

Risk periods are not yet known for COVID-19 vaccines and may depend on the platform as well as latency time of the <<event>> and the time it takes to have a diagnosis of <<event>> in a specific health care system. General recommendations are to have at least 2 months of follow-up for events with short latency, and 3 years for events with long latency.

Figure 1. Cohort design

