9.1.4 Case-crossover (CCO)

Retrospective (multi)-database case-only study that includes subjects who experienced << event >>, independent of vaccination. The CCO design considers the occurrence of << event >> as fixed event and the << COVID-19 vaccine >> exposure random. The design compares the odds of exposure in a specific time window retrospectively in time, where the odds of exposure is compared over these time periods. Index date for the case is the date of the event, index date for the control periods of the same person are distinct points in time prior to case occurrence. Index moment for the control window, should be distanced with at least the duration of the exposure window (**Figure 5**). It is likely that vaccinations will only be administered on weekdays therefore the index date for the control window should be matched on day of the week to have equal probability of exposure. Control periods should not extend in the period prior to launch of the vaccination since the probability of exposure would be zero. Due to unavoidable time trend in vaccination a case time control adaptation is required (Schneeweiss, 1997). The case-time-control design is an elaboration of the case-crossover design, which uses exposure history data from a traditional control group to estimate and adjust for the bias from temporal changes in prescribing.

Figure 5. Case-crossover design

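### For short risk windows starting on the day of the dose, the self-controlled designs do not balance weekdays, so the null rate ratio can exceed 1 if fewer events are recorded at weekends

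*Protocol*

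**What the plan says.** Section 9.1.4 of the protocol (case-crossover) states: "It is likely that vaccinations will only be administered on weekdays". It then requires that "the index date for the control window should be matched on day of the week to have equal probability of exposure". No other design section has a weekday rule.

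The other within-person comparisons are defined as follows.

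- **SCCS (9.1.3.1):** the control time is "All other time within an individual's observation period, that does not fall within the risk period".
- **SCRI (9.1.3.2):** the comparison is with a "control window (a pre-specified time window occurring after the risk window) is calculated". The investigator must fix both windows in advance. The only worked example, under Figure 4, has 42 days of risk and 42 days of control.
- **Same-person comparator (9.1.1):** where the risk period is well known, the comparison time may be the vaccinee's own time after the risk window. The stated caveat is that time trends in events cannot be controlled.

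Short windows are in scope. Section 9.1.1 says that "for the evaluation of anaphylaxis, a risk period of 48 hours should be considered after each vaccine dose". Section 9.1.3 carries this forward: "The risk period depends on the type of event as specified above". Table 2 marks both SCCS and SCRI as suitable for anaphylaxis. Section 9.2.3.3 also asks for risk windows to be split into smaller periods, so even a 42-day window can yield short sub-windows.

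The time-varying confounders listed in 9.2.3.4.2 are age, infections and other vaccines. Table 4 gives conditional Poisson regression for the self-controlled designs, with no weekday term.

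**The concern.** If doses are given only from Monday to Friday, day 0 is never a weekend day and day 1 is one only after a Friday dose. A short window starting at the dose therefore covers fewer weekend days than later time does. The null hypothesis for these designs (9.6.2) is equal incidence in the risk and control periods. If a database records fewer events at weekends, the control rate is pulled down more than the risk rate, and the ratio exceeds 1 with no vaccine effect.

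This would matter most for a safety signal resting on a modest rate ratio. The weekend deficit may also differ between general-practice and hospital sources. The null ratio would then differ by source, and some of the heterogeneity tested under 9.6.3 could be administrative.

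**Working it through.** The protocol gives no figure on this point, so there is nothing to reproduce.

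**Inputs**
- Weekday-only vaccination, from 9.1.4. Uniform spread over Monday to Friday is an assumption.
- A 48-hour risk period, from 9.1.1. In dated records this may be days 0-1 or days 0-2.
- Control time, from 9.1.3.1 and 9.1.3.2: long or whole-week time, or an equal-length window directly after the risk window. The adjacent window is one permitted choice; the protocol does not specify it.
- r, the weekend recording rate relative to a weekday. The protocol does not give it. It is an assumption, shown here from 0.8 to 0.5.

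**Step 1: weekend shares.** Over five equally likely vaccination days, the number of weekend days is 0 on day 0, 1 on day 1, and 2 on each of days 2 to 5.
- Days 0-1: (0+1)/10 = 10%
- Days 0-2: (0+1+2)/15 = 20% (exactly 48 hours from noon also gives 20%)
- Days 1-2: (1+2)/10 = 30%
- Days 2-3: (2+2)/10 = 40%
- Days 3-5: (2+2+2)/15 = 40%
- Whole weeks: 2/7 = 28.6%. SCCS remaining time over 182 or 364 days is 28.6% to 28.8%.

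**Step 2: null rate ratio.** With no vaccine effect,

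RR = [1 − p_risk(1 − r)] / [1 − p_control(1 − r)],

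where p is the weekend share of the window.

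| Risk window | Control time | r = 0.8 | r = 0.5 |
|---|---|---|---|
| Days 0-1 | whole weeks or SCCS | 0.980/0.943 = 1.04 | 0.950/0.857 = 1.11 |
| Days 0-1 | days 2-3 | 0.980/0.920 = 1.07 | 0.950/0.800 = 1.19 |
| Days 0-2 | whole weeks or SCCS | 0.960/0.943 = 1.02 | 0.900/0.857 = 1.05 |
| Days 0-2 | days 3-5 | 0.960/0.920 = 1.04 | 0.900/0.800 = 1.13 |
| Days 1-2 | whole weeks or SCCS | 0.940/0.943 = 0.997 | 0.850/0.857 = 0.992 |
| 42 days | next 42 days | 1.00 | 1.00 |

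At r = 1 every entry is 1.00.

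**Step 3: the aligned window.** Days 7-8 fall on the same weekdays as days 0-1. Both shares are 10%, so the ratio is exactly 1.00 for every r.

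**Step 4: deferred rather than lost events.** Suppose r = 0.5 and the missing weekend events are entered on the following Monday. Monday then has rate 1 + 2 × 0.5 = 2. Day 0 averages (2+1+1+1+1)/5 = 1.2, and day 1 averages (1+1+1+1+0.5)/5 = 0.9. The mean for days 0-1 is 1.05 against a long-run mean of 1.00. The ratio is 1.05 instead of 1.11.

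**The case against.** The strongest objection is that the premise lies outside the protocol. Nothing in it says that fewer events are recorded at weekends. Sections 9.2.3.1 and 9.7 note that general-practice and hospital records differ in what they capture, but do not mention days of the week. For an emergency such as anaphylaxis in hospital data, r may be close to 1. This stands, and it makes the point conditional.

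A reader might infer that the protocol contradicts itself by correcting for weekday vaccination in one design and not in the others. It does not. The case-crossover compares odds of exposure, so weekday-only vaccination biases it directly; the stated purpose of its rule is equal probability of exposure. SCCS and SCRI take vaccinated cases and compare event rates, so they are affected only if event recording also varies by weekday.

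It can also be said that this is a template. Windows are to be specified for each event and design (9.2.3.3), confounders may be added (9.2.3.4.2), and the only SCRI example is unaffected. This is largely right for the SCRI, where an investigator may choose an aligned window, although nothing prompts it. It is weaker for the SCCS, because its control time is defined as all remaining time and Table 4 names the model without a weekday term.

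Case validation (9.2.3.1), lagged event dates (9.6.5) and reporting by source (9.6.3) could expose part of the problem. None of them balances weekdays.

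**Conclusion.** The point holds in a limited form. For short risk windows that include the day of the dose and are not whole weeks, the self-controlled designs and the same-person comparator leave a weekday imbalance that can push the null ratio above 1. At weekend recording of 80% to 50%, the size for days 0-1 is about 1.04-1.11 against SCCS or whole-week control, and 1.07-1.19 against an adjacent two-day control. For days 0-2 against long control it is about 1.02-1.05. These figures assume uniform Monday-to-Friday vaccination and weekend events that are lost; events entered on Monday instead give a smaller ratio against long control.

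Two stronger readings are tempting and not supported. One is that these designs always give a null ratio above 1. The ratio is 1 when recording is even across the week and for windows such as 42/42 days, and it is 0.992-0.997 against long control when day 0 is excluded. The other is that the bias is at least 10% whenever weekend recording is half the weekday rate or less. Days 0-2 against long control give 1.05 at one half.

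This is an inexpensive improvement to the template, not an error in its stated rules.

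**What to change.** **Sections 9.1.3.2 and 9.1.1 (same-person comparator).** State that, when the risk window is not a whole number of weeks, the control window should be offset from it by whole weeks so that each control day has the weekday of a risk day. For days 0-1 this means, for example, days 7-8 or 14-15. The control window must stay outside any risk window, including that of a later dose.

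**Section 9.1.3.1 and Table 4.** For short risk windows or sub-windows, add day of week as a time-varying term in the SCCS conditional Poisson model.

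**Cost.** A sentence or so in each place. The SCRI and the same-person comparator accept a gap of a few days before control time starts. The SCCS carries six extra parameters, which matters only when cases are few. Whole-week windows need no change.

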9.1.4 Case-crossover (CCO)

Retrospective (multi)-database case-only study that includes subjects who experienced << event >>, independent of vaccination. The CCO design considers the occurrence of << event >> as fixed event and the << COVID-19 vaccine >> exposure random. The design compares the odds of exposure in a specific time window retrospectively in time, where the odds of exposure is compared over these time periods. Index date for the case is the date of the event, index date for the control periods of the same person are distinct points in time prior to case occurrence. Index moment for the control window, should be distanced with at least the duration of the exposure window (**Figure 5**). It is likely that vaccinations will only be administered on weekdays therefore the index date for the control window should be matched on day of the week to have equal probability of exposure. Control periods should not extend in the period prior to launch of the vaccination since the probability of exposure would be zero. Due to unavoidable time trend in vaccination a case time control adaptation is required (Schneeweiss, 1997). The case-time-control design is an elaboration of the case-crossover design, which uses exposure history data from a traditional control group to estimate and adjust for the bias from temporal changes in prescribing.

Figure 5. Case-crossover design

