9.1.2 Matched case-control

[figure not shown]
Retrospective (multi)-database case-control study where COVID-19 vaccination status is compared between cases (subjects who experienced << event>>) and controls (subjects who did not experience << event>>) in a specific time window.

Cases and controls should be matched on strong risk factors for the event and we recommend at least: age (year of birth), sex, and database (in case of multiple databases used) as well as calendar time. Controls should arise from a population where prior probability of exposure is the same as for the cases and be eligible to become and observed as a case if they develop the event of interest at a later date. As such persons may serve as control prior to becoming a case and may serve as a control for multiple cases (Richardson, 2004).

Index date for cases should be the disease date (preferably date of onset or first symptoms, otherwise diagnosis), the index date for the controls should be the index date of the corresponding cases. The calendar time matching, controls for confounding due to time related issues (e.g. circulation of SARS-Cov-2). Controls should be sampled using incidence density sampling (Lubin, 1984). For each subject in the database the start and end of follow-up is calculated, exclusion criteria are applied to all subjects and upon occurrence of an exclusion criterion, the follow-up time is censored. For each case, controls subjects who are actively registered in the data source at the index date of the case can be sampled or all eligible controls may be used (recommended if stratified analysis are conducted) (**Figure 2**).

In a case-control study, the aim is to compare the exposure during a specific time window between cases and controls. The time window prior to index date should be disease-specific plus the latency time period for the event under evaluation (e.g. for long latency events). For events with long latency, the risk window should be shortened or divided in small intervals to be able to assess the pattern of risk across different time windows. General recommendations are to have a time window of at least 2 months for events with short latency, and 3 years for events with long latency.

Figure 2. Case-control design

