SCRI	From <<COVID-19 vaccine>> introduction	Subject who received at least 1-dose of COVID-19 vaccine and who experienced <<adverse event>>	Follow-up should begin on the day of vaccine exposure. Length of follow-up will be fixed and depend on the risk and control periods that may vary according to the event. Follow-up may be curtailed if censoring conditions are met.
CCO	From <<COVID-19 vaccine>> introduction	Subject who experienced << event>>	Start: after introduction of <<COVID vaccine>> in a country and other inclusion criteria and are met End: the index date of the event.

⁵Study population for pregnancy outcomes should be adapted and includes pregnant women only, specific inclusion criteria may be required.

Note to future investigators: this section provides guidance and should be adapted according to the type of study design implemented.

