9.2.3.4.2 Confounders

Important confounders are all factors that are known risk factors for the event and are associated with the COVID-19 vaccination. Since both conditions should be fulfilled, we recommend that a list is created of all risk factors associated with the event, which are better known, and the criteria for vaccination eligibility. Accurate assessment and control for confounders is required in signal evaluation studies. The effect of confounders may be minimised by applying matching, adjustment or restrictions. Methods for retaining relevant covariates/confounders in the statistical model may be diverse including stepwise regression or 'change-in-estimate' approach (Greenland, 2016).

Risk factors for events should be obtained from the literature and classified as stable or varying within one individual over the period of the study. Factors associated with vaccination should be obtained from national authorities and may include at-risk conditions or age.

Time varying confounders that should be considered are:

- Age may act as a time-varying confounder in children, depending on the event of interest. Age may be adjusted for the self-controlled designs by dividing person-time during follow-up into pre-specified age groups (e.g., weeks or months)
- Infections (in particular respiratory)
- non-COVID-19 vaccines (in particular influenza)

Special attention should be given to bias related to healthy vaccinee bias and confounding by indication (Remschmidt, 2015).

[Investigator should add confounders relevant to specific events in this section and provide operational definitions & codes].

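### The case-crossover section sets its earliest control window at vaccine launch and does not require case-time-control controls to share the cases' eligibility timing, so a prioritised roll-out can bias the adjusted odds ratio

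*Protocol*

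**What the plan says.** Section 9.1.4 of the protocol sets three rules that bear on this point.

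- Earliest control window: "Control periods should not extend in the period prior to launch of the vaccination since the probability of exposure would be zero". The case-crossover row of Table 3 (section 9.2.2) uses the same country-level bound: "Start: after introduction of <<COVID vaccine>> in a country and other inclusion criteria and are met".
- Equal exposure probability, applied to weekdays only: "the index date for the control window should be matched on day of the week to have equal probability of exposure".
- Adjustment for trend: "Due to unavoidable time trend in vaccination a case time control adaptation is required". The adapted design "uses exposure history data from a traditional control group to estimate and adjust for the bias from temporal changes in prescribing". Section 9.1.4 gives no matching factors for that control group.

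Two other sections matter. On confounders, section 9.2.3.4.2 states: "Factors associated with vaccination should be obtained from national authorities and may include at-risk conditions or age". It also recommends listing the eligibility criteria for vaccination. For the separate case-control design, section 9.1.2 recommends matching on at least "age (year of birth), sex, and database (in case of multiple databases used) as well as calendar time". It also asks that controls come from a population as likely as the cases to have been exposed beforehand. Section 9.1.4 does not refer to either requirement.

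**The concern.** The launch rule is meant to exclude control windows in which vaccination could not have happened. In a staged roll-out, a national launch date excludes only some of them.

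Take 42-day windows, launch on day 0, a person eligible from day 120, and an event on day 155. The case window is days 113 to 155 and the control window is days 71 to 113. The control window lies after launch, so the rule allows it, yet it ends before day 120. The pair can be discordant only towards the case window.

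The case-time-control step divides the case ratio by the same ratio in controls. It corrects for the roll-out only if both groups became eligible at similar times. Conditions that bring early eligibility can also be risk factors for an event under study, and at-risk condition is not among the minimum matching factors in 9.1.2. A mismatch is therefore plausible even after age matching. If cases are eligible earlier than controls, the odds ratio is pulled down and a real safety signal may be masked. If they are eligible later, a signal may be manufactured.

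**Working it through.** The protocol gives no sample size, event count or odds ratio for this design, so there is no figure of its own to reproduce. The check computes expected discordant-pair ratios.

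**Inputs from the protocol.** Launch bound and case-time-control requirement (9.1.4). Window of 42 days, borrowed from the self-controlled risk interval example (9.1.3.2), because 9.1.4 sets no length.

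**Assumptions.** One dose; adjacent windows; no vaccine effect; event day uniform from day 84 to the data cut. A priority group is eligible at day 0 and everyone else at day 120. Eventual uptake is 75% in both groups, so it cancels. 30% of controls are in the priority group. Three uptake curves F after eligibility: exponential (mean 60 days), uniform over 150 days, gamma (shape 3, scale 25 days).

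**Formulas**, for eligibility day E and event day d, with F = 0 before eligibility:

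- case window: 0.75 × [F(d − E) − F(d − 42 − E)]
- control window: 0.75 × [F(d − 42 − E) − F(d − 84 − E)]
- plain odds ratio = sum of case-window probabilities / sum of control-window probabilities
- case-time-control odds ratio = plain ratio in cases / plain ratio in controls

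**Worked example** (exponential curve, data to day 220). Average probabilities (case window, control window) are 0.0741 and 0.1493 in the priority group, and 0.1683 and 0.1040 in the later group.

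- Controls, 30% priority: (0.3 × 0.0741 + 0.7 × 0.1683) / (0.3 × 0.1493 + 0.7 × 0.1040) = 0.1400 / 0.1176 = 1.19
- Cases, 80% priority: (0.8 × 0.0741 + 0.2 × 0.1683) / (0.8 × 0.1493 + 0.2 × 0.1040) = 0.0929 / 0.1402 = 0.66
- Case-time-control odds ratio: 0.66 / 1.19 = 0.56 (true value 1)

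**Range over the three curves**

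| Priority share, cases v controls | Data to day 220 | Data to day 365 |
|---|---|---|
| 30% v 30% | 1.00 | 1.00 |
| 40% v 30% | 0.84–0.90 | 0.95–0.97 |
| 60% v 30% | 0.64–0.72 | 0.83–0.90 |
| 80% v 30% | 0.51–0.62 | 0.70–0.82 |
| 10% v 30% | 1.23–1.55 | 1.06–1.10 |

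**Plain odds ratio among later-eligible cases.** It is 1.6 to 3.1 at day 220. At day 365 it is 1.00 to 1.03, because falling uptake after the group opens pulls the other way.

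**Second set of assumptions.** Three groups opening at days 0/30/60, 0/60/120 or 0/90/180; daily vaccination hazard 0.01 to 0.03; events on days 84 to 300.

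- Between 1% and 49% of control windows lie wholly before the person's eligibility, and a further 6% to 17% partly.
- With equal eligibility mix the case-time-control odds ratio is 1.00, even with 39% of control windows wholly impossible.
- Cases mainly early: 0.65 to 0.85. Cases mainly late: 1.13 to 1.39.
- For a true odds ratio of 2 (equal vaccination speed across groups): 1.30 to 1.69 and 2.31 to 2.70.

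**Which change removes the bias**

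- Restricting windows to the person's eligible time, with controls still pooled: in the two-group model at day 220, 0.83 to 1.00 (80% v 30%) and 1.00 to 1.25 (10% v 30%). In the three-group model it gives 1.00 if vaccination speed is equal across groups, but 0.73 to 1.34 if speed differs. In some of those runs the direction reverses, for example from 0.85 to 1.34.
- Stratifying controls on eligibility group: 1.00 (2.00 for a true value of 2) in every group-specific computation, even with the launch bound kept.

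**The case against.** A reader might infer that the impossible windows in themselves bias the case-time-control odds ratio. The calculation does not support that. With equal eligibility mix the ratio is 1.00, so the bias comes from the mismatch between cases and controls, not from the launch sentence alone.

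The strongest defence is that 9.1.2 is the protocol's fullest account of control selection. It asks for equal prior probability of exposure and for matching on strong risk factors, with the listed factors only a minimum. Read into 9.1.4, that would close the gap. Year-of-birth matching would also cover a purely age-based roll-out. This softens the point, but 9.1.4 makes no cross-reference, and age matching does not cover at-risk conditions.

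The larger figures are stress cases, and that objection stands. A 30-day eligibility gap with 40% v 30% gives 0.96 to 0.98; a 60-day gap with 50% v 30% gives 0.88 to 0.89. With 2-day windows, as for the 48-hour anaphylaxis period in 9.1.1, even 80% v 30% gives 0.97 to 0.99 at day 220, depending on the first event day allowed.

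Finally, this is a template. Table 3 is to be adapted, its row leaves other inclusion criteria open, section 9.3 asks for the vaccination strategy, and section 9.8 and Annex 3 already limit this design when exposure has time trends. None of these states the rule. Section 9.1.4 answers the trend problem by requiring the case-time-control step, so the composition of its control group has to be right.

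**Conclusion.** The point holds in a conditional form. The launch or country-level bound falls short of the reason given for it whenever eligibility is staged. The unadjusted odds ratio is then pushed upward for later-eligible cases, most visibly early in the roll-out. The required adjustment repairs this only when its controls share the cases' eligibility timing, which 9.1.4 does not secure.

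With 42-day windows and no vaccine effect, the adjusted odds ratio is about 0.84 to 0.97 for a mild mismatch. It is about 0.5 to 0.8 (80% v 30%) or 1.06 to 1.55 (10% v 30%) for large ones. It is 1.00 with no mismatch and close to 1 with very short windows. Eligibility dates, uptake curves, priority shares and window length are all assumptions, so these figures show what is possible and do not predict the bias in any particular study.

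Two stronger inferences are not supported: that every case-crossover analysis under this template is biased, and that moving the window bound would be enough. Nor does the protocol overlook eligibility, since 9.2.3.4.2 asks for it. It does not carry it into the case-crossover rules.

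**What to change.** **Main change, section 9.1.4.** State that case-time-control controls must be matched or stratified on vaccine-eligibility group (age band, at-risk condition, region) as well as calendar time, and that the 9.1.2 requirement of equal prior probability of exposure applies to them. The cost is a sentence or two of text and one derived variable per data source, built from information that 9.2.3.4.2 and 9.3 already request. Where at-risk conditions are poorly recorded, some mismatch will remain and should be acknowledged.

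**Secondary change, section 9.1.4 and the Table 3 case-crossover row.** Define the earliest control window as the date the person's own priority group became eligible, instead of national launch, in the main analysis or as a sensitivity analysis. This makes the rule meet its stated reason. Events within two window lengths of eligibility are lost (84 days with 42-day windows), which falls on the early roll-out data. It should accompany the main change and not replace it.
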